## **AIMS:**

### **Aim 1. Acceptability, feasibility and safety of a yoga program for chronic pain in SCD.**

We will assess the acceptability of yoga for chronic pain in SCD. We will also assess the feasibility and safety of a yoga program for adolescents with SCD and chronic pain.

**Rationale:** Yoga content customized for patients with SCD chronic pain, is currently not available for patients. We propose for the first time to develop routines with consideration of needs, expectations and physical limitations of SCD. The overall acceptability, feasibility and safety of such a program in SCD is yet to be studied, though data from other chronic painful and inflammatory conditions do not suggest safety concerns.

**Hypotheses:** 1a) We hypothesize that more than >50% of those with chronic pain approached to complete a survey of their attitudes and practices related to yoga, would be willing to complete a survey. 1b) At least 50% of adolescent SCD patients with chronic pain offered participation in a yoga program through in-person yoga sessions will agree to participate in the yoga program 1c) At least 80% of participants enrolled in the in-person yoga program will be

able to attend at least 6 of 8 in-person yoga sessions. 1d) Fewer than 30% of participants will have an ED visit or hospitalization for pain within 24 hours of completion of a yoga session.

**Aim 2: Feasibility of collection of psychological and patient-reported outcomes in a study of yoga for chronic pain in SCD.**

**Rationale:** Yoga content tailored and customized for patients with SCD chronic pain, is currently not available for patients. We propose for the first time to develop routines with consideration of individual needs, expectations and physical limitations. In addition to aims in Aim 1, we propose to measure health outcomes and psychological characteristics pre- and post- the yoga program, with a goal to determine the feasibility of collection of these outcomes in a larger study. Since our sample size is small, and this is a pilot feasibility study, it will not be powered to assess measurable benefit (or lack of) from the yoga program, therefore these outcomes will be exploratory. These outcomes will be collected regardless of the number of yoga sessions attended.

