**Outcome Measures:**

**The study will have the following primary outcome measures:**

- 1- Proportion of adolescent patients with SCD and chronic pain approached that consent to participate in Part A.  
*The study hypothesis is that the proportion of adolescent patients with SCD and chronic pain approached that consent to complete a survey to assess attitudes and practices related to yoga (Part A) will be 50% or greater.*
- 2- Proportion of adolescent patients with SCD and chronic pain enrolled in Part A that consent to participate in Part B.  
*The study hypothesis is that the proportion of adolescent patients with SCD and chronic pain enrolled in Part A that consent to participate in Part B will be 50% or greater.*
- 3- Proportion of participants enrolled in Part B that attend at least 6 of 8 yoga sessions.  
*The study hypothesis is that the proportion of participants enrolled in Part B that attend at least 6 of 8 in-person yoga sessions will be 80 percent or greater.*
- 4- Proportion of participants enrolled in Part B with an ED visit or a hospitalization for pain within 24 hours of completion of each yoga session.

*The study hypothesis is that the proportion of participants enrolled in Part B with an ED visit or a hospitalization for pain within 24 hours of completion of each yoga session will be 30% or less.*

- 5- Proportion of participants in Part B who complete all study assessments.  
*The study hypothesis is that the proportion of participants who complete all study assessments before, and at the end of the yoga program will be 70% or greater.*
- 6- Adherence to submission of pain diary.  
*The study hypothesis is that the proportion of participants who submit at least 4 days of pain diary data before, and at the end of the yoga program will be 70% or greater.*

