### **PART B: Feasibility and Safety of a yoga program for SCD.**

Part B will assess the feasibility and safety of a yoga program for SCD. This program will comprise of 8 instructor-led group yoga sessions. We will measure psychological factors implicated in chronic pain and pain-related patient reported outcomes, and assess the feasibility of collection of these outcomes. We will also explore patient acceptability of yoga through qualitative interviews and conduct a needs assessment for the development of a smartphone app for yoga.

Participants who express interest in learning more about participating in a study of yoga in Part A will be offered this portion of the study.

Prior to enrollment in Part B, the investigators will confirm with their treating provider that the patient does not meet any exclusion criteria for the study. If any concerns are noted at this point, then patient will not be enrolled on Part B of the study, and this will be documented.

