- vi. Proposed Yoga protocol (45-60 minutes), but this may be modified as yoga instructor deems necessary to suit patients with SCD. The sequence below is only to serve as a guide, and only lists representative elements, and instructor may move around the order. The final yoga protocol may be modified in-real time per instructor discretion, and to maintain safety, based on ongoing feedback and response to classes. It is possible that some elements of the yoga sessions may change as classes progress.

- a) Opening and Pranayama (breathing exercises)
  - b) Gentle warm up
  - c) Predefined set of standing and poses
  - d) Surya (Sun), Chandra (Moon) and earth series of poses
  - e) Pranayama (Breathing exercises)
  - f) Guided relaxation or 'yoga nidra'
- vii. During, and at the end of each session, feedback will be obtained from participants as a group, and will be recorded. Future yoga sessions may be modified as necessary based on participant feedback.
- viii. Email or phone reminders for upcoming yoga sessions will be sent to participants at the email address/phone numbers provided. If participants miss or are unable to attend sessions, study staff may follow up to attempt to determine reason for non-attendance.
- ix. Study staff will also record ED visit or hospitalization that occurred in the 24 hours following the yoga session. This will be assessed 24 hours after, but prior to the start of the subsequent session.

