#### **Total number of participants:**

*Part A, Group 1: Up to 40 adolescent patients who meet inclusion/do not meet exclusion criteria. Patient participants will be enrolled on Part A (up to a max of 40 patient participants) until 20 patient participants enroll on Part B.*

*Part A, Group 2: Up to 40 parents/guardians of adolescent patients in Group 1. The number of Group 2 participants will be determined by the number of Group 1 participants. Only one parent/guardian per Group 1 participant will be enrolled.*

*Part B, We anticipate enrolling up to 20 patients in Part B of the study.*

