All questions will be answered by a member of the research team and/or the PI. If the individual agrees to participate, he/she will be consented/assented in person. A copy of the signed consent will be given to the participant.

Participants will be consented for Part A and Part B separately. For those who are enrolled in part B of the study, investigators will confirm that patients don't have exclusion criteria prior to proceeding with the first yoga session.

Flyers may be posted in the sickle cell clinics and at community sites, or in on-line patient forums, with study coordinator contact information.

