#### **Anticipated results and Potential problems, alternate strategies:**

We may encounter difficulties with enrollment of participants. Participants may be uninterested in complementary therapies or may believe that they may not help with chronic pain. They may not want to pursue yoga as a complementary therapy due to concerns that this may be in

conflict with their religious beliefs. There may be cultural barriers to acceptability of yoga. The yoga instructors or investigators, who are familiar with addressing concerns about yoga, will be available to answer any questions they may have about the practice of yoga itself and if potential participants have any concerns regarding yoga as a spiritual practice.

Once enrolled in Part A, participants may not complete survey, though we expect that this non completion rate will be low. Once enrolled on part B, participants may decide not to participate further in the study, or may have a medical complication between enrollment and participation in the yoga sessions that may not allow them to participate in the study. Participants may not attend one or more in-person yoga sessions. We will attempt to determine the causes for individuals dropping out of the program.

There may also be discontinuation of the program due to increased pain, or perceived increased pain, and this will also be noted as a reason for discontinuation. Systematic reviews have not shown increased risk of severe adverse events by the use of yoga in the management of chronic pain syndromes. In addition, there may be changes in health status that may prevent safe continuation of the yoga program. These aims will generate critical data on the feasibility acceptability, reach and maintenance of yoga in adolescents with SCD and chronic pain.

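### Primary safety outcome 4 counts Part B enrollees who attend no session as event-free, has no rule for combining eight sessions, and differs from hypothesis 1d in session wording and threshold

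*Combined protocol and SAP*

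**What the plan says.** Under Outcome Measures, primary outcome 4 is expressed as a proportion: "participants enrolled in Part B with an ED visit or a hospitalization for pain within 24 hours of completion of each yoga session". Its hypothesis is that the proportion "within 24 hours of completion of each yoga session will be 30% or less". Under Aim 1, hypothesis 1d covers the same ground in other terms: "Fewer than 30% of participants will have an ED visit or hospitalization for pain within 24 hours of completion of a yoga session".

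Part B offers eight sessions. On size, Total number of participants says: "We anticipate enrolling up to 20 patients in Part B of the study". On collection, item ix of In-person yoga sessions says: "Study staff will also record ED visit or hospitalization that occurred in the 24 hours following the yoga session". Analytic Methods foresees descriptive statistics for Part B and repeats that these visits are recorded. It gives neither a denominator nor a way of summarising over sessions.

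Three places bear on whether an enrollee might never be exposed:

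- The section on anticipated results and potential problems foresees enrollees who choose not to continue, or who "may have a medical complication between enrollment and participation in the yoga sessions".
- Recruitment Methods has investigators verify that Part B patients do not "have exclusion criteria prior to proceeding with the first yoga session".
- The Part B section places a check before enrollment, at which "the investigators will confirm with their treating provider that the patient does not meet any exclusion criteria". This limits late exclusions but cannot prevent a later withdrawal or a new complication.

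**The concern.** **Denominator.** The event exists only after a completed session. On the any-session reading, someone who attends none cannot have it but still counts below the line. The reported figure is then the risk among attenders multiplied by exposed/enrolled. This can only lower it, so any error is toward apparent safety. No section says how non-attenders are handled; that they count as event-free follows from the stated denominator.

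**Combining rule.** Outcome 4 refers to each session and hypothesis 1d to a session. The text could mean at least one event per participant over all sessions, a separate figure for every session, or, literally, an event after all of them. On the per-session reading every absence, not only complete non-attendance, enters the denominator as event-free.

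**Threshold.** Exactly 30% meets the hypothesis for outcome 4 and fails hypothesis 1d.

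Because the benchmark is explicit, the same records could be reported as meeting or missing it, with the reading settled after the results are known.

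**Working it through.** The plan gives no sample-size, power or error-rate calculation for this outcome, so there is no figure of its own to reproduce beyond the 30% benchmark. From the documents: N up to 20 in Part B, eight sessions, thresholds of ≤30% (outcome 4) and <30% (1d). Assumed, because the documents do not give them: the number never exposed (u = 0 to 8), the risk among attenders (10% to 40%), the risk per session (2% to 10%) and the within-participant correlation (0, 0.2, or complete).

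**1. Denominator, any-session reading, N = 20.** Attenders m = 20 − u. The attender risk that reads as 30% is 0.30 × 20 / m = 6/m. A verdict changes at an event count x if x/20 and x/m fall on different sides of the threshold. The chance of such a count uses X ~ Binomial(m, p), at p = 10%, 20%, and 30–40%.

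| u | Attender risk read as 30.0% | Counts changing the outcome 4 verdict | Chance at 10% / 20% / 30–40% | Counts changing the 1d verdict |
|---|---|---|---|---|
| 0 | 30.0% | none | 0 | none |
| 1–3 | 31.6–35.3% | 6 | 0.4–0.7% / 7–10% / 15–20% | none |
| 4–6 | 37.5–42.9% | 5, 6 | 0.9–1.7% / 12–18% / 32–41% | 5 |
| 7–8 | 46–50% | 4, 5, 6 | 2.6–3.4% / 20–25% / 47–62% | 4, 5 |

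For u = 4–6 the chance that the 1d verdict changes is 0.8–1.4%, 9–12% and 16–22% at the same risks. As examples, 6 events are 6/20 = 30.0% but 6/19 = 31.6%, and 5 events are 5/20 = 25.0% but 5/16 = 31.3%.

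With N = 19, u = 1–2 changes nothing. With u = 3–4 either verdict changes only at 5 events (chance 1.0–1.4%, 10–12%, 16–21%).

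**2. Combining rule, eight sessions attended.** With risk p per session:

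- Independent sessions: any-session risk = 1 − (1 − p)^8.
- Correlation 0.2 (beta-binomial with a = 4p, b = 4(1 − p)): any-session risk = 1 − ∏ (b + j)/(4 + j), j = 0 to 7.
- Complete clustering (the same participants have every event): any-session risk = p.

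| Risk per session | Independent | Correlation 0.2 | Complete clustering |
|---|---|---|---|
| 2% | 15% | 9% | 2% |
| 5% | 34% | 21% | 5% |
| 10% | 57% | 39% | 10% |

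The any-session figure reaches 30% at p = 1 − 0.7^(1/8) = 4.4% with independence, and at 7.3% with correlation 0.2. At p = 5%, independence and 20 participants, the chance of at least 7 events (above 30%) is 0.53 on the any-session reading and 0.00003 for a single session.

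**3. Threshold.** The two forms differ only when 0.30 × N is a whole number. For N up to 20 that means N = 10 (3 events) or N = 20 (6 events); at N = 11–19 they cannot disagree. At N = 20, P(X = 6) is 0.9%, 11%, 19% and 12% at true risks of 10%, 20%, 30% and 40%.

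**The case against.** The best counter-argument concerns weight. The denominator matters little if few people attend nothing: u = 0 has no effect, and u = 1–3 at N = 20 changes the outcome 4 verdict only at exactly 6 events and the 1d verdict never. Outcome 3 expects at least 80% to attend six or more sessions. At N = 20 that is 16 people, leaving room for at most 4 never-attenders, so u of 5 or more would mean outcome 3 had already failed visibly. The larger values of u are therefore extreme cases, and u = 1–4 is the range to keep in mind. This stands.

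It is also fair that requiring an event after every session is not a credible safety definition. One proportion with one benchmark, together with the wording of 1d, favours the any-session reading. That remains an inference, because the formal outcome definition says each session. The real ambiguity is any-session versus per-session, and it remains open.

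The analysis is descriptive, with no test or go/no-go decision attached, and the attender figure could be calculated from planned data. But nothing commits the investigators to report it, and in a descriptive study the definition of the proportion is the analysis.

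Finally, dividing by those who attended at least once still gives a one-session attender the same weight as an eight-session attender. That is correct, and it is why the rate per attended session belongs alongside.

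**Conclusion.** The concern holds on all three points and should be fixed. The textual facts are clear: the denominator is everyone enrolled in Part B, no combining rule exists, and 1d and outcome 4 differ in session wording and inequality.

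The size depends on assumptions about exposure and risk that the documents do not supply. The combining rule can have the largest effect, since under moderate clustering or less the same events can fall on either side of 30%; under complete clustering the readings coincide. The denominator effect is nil with no never-exposed enrollees, modest with one to three, and larger from four upward, always toward apparent safety. The threshold conflict is confined to 3 of 10 or 6 of 20.

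The consequence is for what is reported and concluded about safety. Safety monitoring during the study does not depend on this outcome.

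**What to change.** Define outcome 4 as the number of participants with at least one ED visit or hospitalization for pain in the 24 hours after any session they attended, divided by the number who attended at least one session, with an exact 95% confidence interval. As supplements, report the figure over all enrolled, the number never exposed, and the event rate per attended participant-session.

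Use the same session wording and a single form of the threshold in Aim 1 (hypothesis 1d), Outcome Measures and Analytic Methods. Which form is for the investigators to choose.

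The halting statement under Monitoring of Potential adverse outcomes uses ≥30%, states no 24-hour window and refers to increased pain leading to a visit. It is a different quantity, but 6 of 20 would satisfy the outcome 4 hypothesis while 30% is also the halting percentage. The investigators must reconcile these passages.

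The cost is wording and a few descriptive rows. Attendance is already needed for outcome 3 and post-session visits are already recorded. The price is a somewhat smaller denominator, a wider interval (exact 95% limits 9–49% for 5/20 against 11–59% for 5/16) and possibly a less favourable percentage.

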Lack of awareness and access to yoga are barriers to the use of yoga, and smartphone apps may overcome this barrier. Limited health knowledge is one of the reasons for non-use of complementary therapies, and individuals with lower educational attainment, and lower income were more likely to report lack of knowledge as a reason for non-use of these therapies. There are increased challenges in access to yoga for minority and low-income populations, since yoga is often a fee-based service and there may be additional limitations due to geographical access.

While there is currently no data on the use of yoga as a Complementary and Alternative Medicine (CAM) therapy in SCD chronic pain, one study in acute SCD pain suggest that the practice was well accepted and well tolerated. Additionally, preliminary data from a secondary data analyses of the decision aid study suggests that adult patients express a desire for non-medication based pain relief. These data indicate that patients with SCD who suffer from chronic pain, may be willing to consider CAM therapies. A customized yoga program, taking into account risks of SCD, and limitations posed by SCD-related comorbidities, including but not limited to fixed deformities, AVN, splenomegaly, lung disease, cerebral vasculopathy, retinopathy, etc.

The overarching goal of this study is to 1) determine the acceptability of yoga for chronic pain in SCD 2) determine the feasibility of a yoga program for individuals with SCD chronic pain, 3) determine the safety of a yoga program for individuals with SCD chronic pain, 4) determine the feasibility of collection of psychological and patient reported outcomes in a study of yoga for chronic pain and 5) Explore patient acceptability of yoga through qualitative interviews and conduct a needs assessment for the development of a smartphone app for yoga.

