#### **Exclusion Criteria:**

- 1-Daytime or nighttime oxygen requirement for hypoxia
- 2-Most Recent Hemoglobin< 5 or platelet count < 20
- 3- Known Pregnancy

- 4- Severe cognitive issues not allowing for understanding consent/ assent and instructions
- 5- History of overt stroke with significant residual motor weakness
- 6-History of recurrent syncope
- 7- Any other comorbidities or health concerns that the treating healthcare provider or investigators feel are a contra-indication for participation in the study.

The presence of the following conditions will be assessed from the medical record but are **NOT** exclusion criteria: 1) Presence of splenomegaly, 2) presence of asthma 3) presence of AVN 4) Presence of cerebral vasculopathy 5) retinopathy, 6) presence of symptomatic pulmonary HTN. The assessment of the study investigators and the treating team will determine if any of these or any other co-morbidities require for modification of or pose as potential contraindications for participation in a yoga program.

If prospective study participants are enrolled on other clinical trials that do not allow for concurrent enrollment in this study, they will not be enrolled on this study. The PI/study staff will confirm eligibility for enrollment with PI's/study staff of the respective clinical trials regarding patient eligibility for enrollment.

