#### **Monitoring of Potential adverse outcomes:**

**Pain:** There is a potential for increased discomfort and/or pain as a result of the yoga poses, even though the program is designed to be gentle. The potential for increased pain will be discussed with the participant during the consenting session and if needed, prior to each in-person yoga session, so the patient and their family are fully informed of the potential risks. Pain may result in increased use of medication, or potentially a ED visit, or hospitalization. We will also track healthcare utilization for pain, and if  $\geq 30\%$  of participants present with increased pain resulting in an ED visit or hospitalization, we will halt yoga sessions and reassess if any changes need to be made to the protocol. Since participants have chronic pain, it may be difficult to determine if the yoga program was the cause of increased pain, so we will go by patient self-report to determine if yoga program was believed to be causative. If this is the case, the participant may opt to discontinue the research study or a physician researcher may opt to withdraw the participant. We also anticipate that those who perceive an increase in pain following the program will self-discontinue from the study. Monitoring during yoga sessions will make every effort to ensure participants do not exceed their limitations.

**Other risks:** There is a possibility of muscle strain, of aggravation of an existing injury, which may cause discomfort or pain, increased medication use, need for medical treatment, increased time off work or school, or financial loss.

As with all research studies, there is also a risk of loss of confidentiality of participant data.

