### **Analytic Methods:**

Part A: Descriptive statistics will be used to determine the proportion of patients with chronic pain who are willing to consider yoga and participate in a yoga program. We will also determine predictors of acceptability of yoga such as, but not limited to, age, gender, pain phenotypes, medical comorbidities, attitudes towards complementary therapies, fear of movement and pain catastrophizing. There may be additional analyses that may be conducted once these are completed.

Part B: This aim will also determine the feasibility of attendance at in-person yoga program, and safety. As in part A, we anticipate descriptive statistics will be utilized, and we will look for characteristics associated with feasibility of attendance at in-person yoga sessions. Qualitative analysis will also help indicate wider issues related to acceptability of yoga and barriers to use of yoga and other complementary therapies. Qualitative analyses will also analyze participant needs for development of a yoga app.

We will monitor for adverse effects following the in-person yoga session. If the research coordinator receives reports of increased pain in participants following a yoga session, that are perceived to be related to the yoga session, then these will be recorded. We will also record any ED visits or admissions for pain that occur within 24 hours of the yoga session. We will monitor for drop out from the study due to perceived increase in pain.

Pain diary data and quality-of-life survey and PROMIS will interrogate improvement in pain, quality-of-life from the use of yoga application program. Given the pilot nature of this study, we do not expect we will be adequately powered to detect differences in health outcomes like pain intensity and pain interference or psychological factors between pre- and post treatment values. There may be additional analyses that may be conducted once these primary analyses are completed.

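### The only pre-specified safety proportion counts pain visits alone; visits for any cause, which staff are already told to record, should be reported beside it

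*Combined protocol and SAP*

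**What the plan says.** Safety is among the goals listed in Background and Significance, and again in Aim 1 and in the purpose of Part B. The plan attaches one proportion to it.

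- **Aim 1, hypothesis 1d:** "Fewer than 30% of participants will have an ED visit or hospitalization for pain within 24 hours of completion of a yoga session".
- **Outcome Measures, primary outcome 4:** the proportion of Part B participants "with an ED visit or a hospitalization for pain within 24 hours of completion of each yoga session", with the hypothesis that it "will be 30% or less".
- **Analytic Methods, Part B:** "We will also record any ED visits or admissions for pain that occur within 24 hours of the yoga session".
- **Monitoring of Potential adverse outcomes:** if at least 30% "of participants present with increased pain resulting in an ED visit or hospitalization, we will halt yoga sessions" and reassess.
- **In-person yoga sessions, item ix:** "Study staff will also record ED visit or hospitalization that occurred in the 24 hours following the yoga session". This instruction does not mention the cause of the visit.

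On comorbidity, Background and Significance says a customized program should take account of SCD-related conditions, "including but not limited to fixed deformities, AVN, splenomegaly, lung disease, cerebral vasculopathy, retinopathy, etc". The Part B Exclusion Criteria name six conditions that are noted from the record but do not exclude: splenomegaly, asthma, AVN, cerebral vasculopathy and, in the plan's numbering, "5) retinopathy, 6) presence of symptomatic pulmonary HTN". The investigators and the treating team judge whether any of them calls for modification or is a contraindication.

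The risks of yoga that the plan names, in the monitoring section and under Potential Risks, are increased pain, muscle strain and aggravation of an existing injury.

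**The concern.** The plan screens participants on non-pain grounds and then measures safety on pain alone. Someone who needs emergency or inpatient care within a day of a session for a respiratory, neurological or splenic problem, without pain as the reason, adds nothing to the numerator of outcome 4 and stays in its denominator.

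Pain visits are also hard to interpret on their own here. Entry requires pain on at least 15 days a month, recruitment may draw on patients who already use care often for pain, there is no control group, and the monitoring section concedes that attributing increased pain to yoga may be difficult. At stake is whether a statement that the safety hypothesis was met describes safety or only pain-related use of care.

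**Working it through.** The documents give no event rate, power or sample-size derivation for outcome 4, so there is no figure of the plan's own to reproduce. The check is a comparison of definitions, followed by an illustration of size.

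**Step 1: which events each section covers**

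| Section | Event | Pain only? |
|---|---|---|
| Aim 1, hypothesis 1d | visit within 24 hours of a session | yes |
| Outcome Measures, outcome 4 | same | yes |
| Analytic Methods, Part B | visits recorded within 24 hours | yes |
| Monitoring, 30% trigger | increased pain leading to a visit | yes; not tied to 24 hours |
| Assessments, item 7 | health care use up to 6 months after the program | yes |
| In-person yoga sessions, item ix | visit within 24 hours | no qualifier |

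Grammatically, the words on pain in outcome 4 could attach to hospitalization only. The monitoring section ties both kinds of visit to increased pain, which supports the pain-only reading. None of the other primary outcomes and none of the six exploratory outcomes counts a non-pain event. Item ix may therefore capture such events, but they feed no outcome.

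**Step 2: what the definition does to the proportion**

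Input: n = 20, the planned maximum for Part B. The event counts are invented for illustration.

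- 5 participants with pain visits: outcome 4 = 5/20 = 25%.
- 2 other participants with non-pain visits only: outcome 4 is still 5/20 = 25%.
- Any cause: (5 + 2)/20 = 7/20 = 35%.

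**Step 3: how often there would be something to miss**

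Assumptions: per-participant risk over the program of p for a pain visit and q for a non-pain visit, independent of each other. Neither comes from the documents.

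- Chance of at least one participant with a non-pain visit = 1 − (1 − q)^20.
- Expected participants with a non-pain visit only, absent from the numerator of outcome 4 = 20 × q × (1 − p).

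| q | At least one in 20 | Expected missed, p = 15% |
|---|---|---|
| 2.5% | 1 − 0.975^20 = 0.397 | 20 × 0.025 × 0.85 = 0.425 |
| 5% | 1 − 0.95^20 = 0.642 | 20 × 0.05 × 0.85 = 0.85 |
| 10% | 1 − 0.90^20 = 0.878 | 20 × 0.10 × 0.85 = 1.7 |

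With p from 10% to 25% and q from 2.5% to 10%, the expected number missed runs from 20 × 0.025 × 0.75 = 0.375 to 20 × 0.10 × 0.90 = 1.8.

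**Step 4: sensitivity only**

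The plan sets no limit for visits of any cause. If the pain limit in Outcome Measures (at most 0.30 × 20 = 6 participants) were nevertheless used for both, with any-cause risk 1 − (1 − p)(1 − q) and exact binomial probabilities:

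- p = 15%, pain only: P(X ≤ 6) = 0.978.
- p = 15% with q = 2.5%, 5% or 10%: any-cause risk 17.1%, 19.3% or 23.5%; P(X ≤ 6) = 0.958, 0.927 or 0.831.
- p = 25%, q = 10%: 0.786 for pain only against 0.511 for any cause (risk 32.5%).

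**The case against.** The strongest answer is that a pain-focused outcome matches the main risk the plan names, that this is a descriptive single-arm pilot of at most 20 participants, and that other arrangements cover the rest. Much of this stands.

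- **Named risks.** A reader might infer that the plan identifies SCD complications as risks of yoga and then ignores them. It does not. They appear as comorbidities to account for or as possible contraindications. The treating provider confirms eligibility before Part B, and patients with an oxygen requirement, recurrent syncope, or overt stroke with significant residual motor weakness are excluded. Some listed conditions, such as AVN, could present as pain and would then be counted.
- **Visibility.** A reader might infer that serious non-pain events would go unseen. That is too strong. Analytic Methods commits to monitoring adverse effects after sessions without limiting this to pain, a physician attends each session, the interviews ask about perceived harms, and the investigators meet every two weeks. None of these, however, defines a non-pain event or commits to reporting a count.
- **Contradiction.** Item ix and Analytic Methods can be read together as broad collection with a narrower analysis, since the latter does not say that only pain visits are recorded. Still, staff who worked from Analytic Methods alone could leave a non-pain visit unrecorded.
- **Size.** The 5 + 2 example is constructed. At 15% pain risk and 2.5% non-pain risk, the Step 4 probability moves only from 0.978 to 0.958. Nor do the documents support a claim that non-pain events are rarer than pain visits or more specific to yoga.

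**Conclusion.** The point holds as a gap in what is counted and reported. The sole pre-specified safety proportion is limited to pain, so the safety hypothesis can be met without non-pain emergency or inpatient care appearing in it, although determining safety is a stated goal. This follows from the wording and needs no assumption about rates.

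The size cannot be fixed from the documents. Under the assumed risks, outcome 4 would omit about 0.4 to 1.8 participants of 20 on average, and the chance of at least one non-pain event would be 40% to 88%. Those figures rest on full Part B enrolment, independent events and risks chosen for illustration. A reader might take 35% for any cause as a failed safety hypothesis. The documents do not support that, because the 30% limit was set for pain visits. This is a cheap improvement to the plan, not a flaw that invalidates outcome 4.

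**What to change.** 1. Leave outcome 4 and its 30% threshold unchanged.
2. Report beside it the proportion of Part B participants with an ED visit or hospitalization for any cause within 24 hours of an attended session, without a pass limit, and list each non-pain event by diagnosis.
3. Reconcile Analytic Methods, Part B, with item ix of In-person yoga sessions, so that both say all such visits are recorded and the cause is noted.
4. State that the safety conclusion will rest on both results.

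The cost is a few sentences. Item ix, read as written, already has staff record the visits. The downside is that the reported safety picture may look slightly less favourable. No clinical rule needs to change for this.
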